3.2 Allocation to Treatment Groups and Blinding

Children will be randomized to receive early literacy promotion or standard literacy promotion. Randomization sequences will be developed by the project biostatistician using computer-generated random numbers prior to study enrollment and will be placed in sealed opaque envelopes. The control group will not receive the early literacy promotion program, and will instead receive standard literacy promotion over the course of the study beginning at 6 months of age.

3.3 Study Duration, Enrollment and Number of Sites

3.3.1 Duration of Study Participation

The study duration per subject will be approximately 2 years following screening/consenting. For the sub-study, study duration will be for approximately 1 hour per participant with a 1 hour follow up focus group to triangulate findings and themes.

3.3.2 Total Number of Study Sites/Total Number of Subjects Projected

The study will be conducted at the Karabots Primary Care Center in Philadelphia, Pennsylvania, which has already implemented ROR as standard practice. This site has been individually recruited to participate (see PeRC letter of support) and has agreed to participate.

Recruitment will stop when approximately 240 subjects (120 dyads of parent and infant) are enrolled. For the qualitative component, recruitment for the semi-structured interviews will stop once 30 parents are enrolled or sooner if thematic saturation is achieved with fewer participants.

3.4 Study Population

3.4.1 Inclusion Criteria

- 1) English or Spanish speaking
- 2) Parents 15 years of age or older at the start of the study
- 3) Child born \geq 35 weeks estimated gestational age
- 4) Child less than 4 weeks old at enrollment
- 5) Child with Medicaid Insurance
- 6) Phone with text messaging plan

3.4.2 Exclusion Criteria

- 1) Child born premature $<$ 35 weeks EGA
- 2) Children with neurodevelopmental disabilities or congenital malformation at increased risk of language delays

3.4.3 Inclusion Criteria for Sub-study

- 1) Already enrolled in main study in the control group.
- 2) Parents enrolled in the control group with infants less than 6 months of age or not having 6 month well child visit.

3.4.4 Exclusion Criteria for Sub-study

- 1) Not enrolled in main study in the control group

- 2) Parents enrolled in the control group with infants older than 6 months or already having their 6 month well child visit.

Subjects that do not meet all of the enrollment criteria may not be enrolled. Any violations of these criteria must be reported in accordance with IRB Policies and Procedures.

3) STUDY PROCEDURES

a. Screening/Consenting Visit and Study Visit 1

- Identify eligible newborns at the time of their first well child visit using the electronic health record (EHR)
- Recruit and consent eligible newborns and their parents at well child visits prior to 1 month of age
- Randomize newborns and their parents into intervention and control groups
- Collect baseline demographic, parent adversity, and parent mental health information
- Eligible parents for the semi-structured interviews will be identified after enrollment in the study. These parents will be notified regarding this separate component of the study, and those who are interested will receive additional informed consent to participate in the qualitative portion of the study. The qualitative interviews will be conducted during the first year of study with aims of 30 interviews or until thematic saturation is achieved.

b. Study Treatment Phase (enrollment until 4 month well-child visit)

- Conduct semi-structured interviews up to six months of age and follow up focus group
- Make reminder phone calls to all participants to schedule well visits
- Implement an EHR alert to remind clinicians of patients in intervention group at time of well visits at 1 month, 2 months, 4 months, and 6 months
- Provide developmentally appropriate books and reading script to clinicians to give to the members of the intervention group at enrollment, 1-month, 2-month and 4-month well visits
- Implement 24 weekly text message reminders about reading for intervention group
- Implement 24 weekly text message reminders about safety for control group

c. Follow-up Visits (at 6-, 12-, 18-, and 24- month well visits)

- Conduct semi-structured interviews up to six months of age

- Make reminder phone calls to all participants to schedule well visits
- Implement an EHR alert to remind clinicians of patients in both groups at time of well visits
- Schedule and complete study visits in conjunction with well visits at 6, 12, 18, and 24 months of age
 - Parents will complete measures of reading activity (Stim-Q) at each study visit.
 - Children will complete measure of child expressive and receptive language development (Preschool Language Scale-V) at 6- and 24-month visits.
 - At the 12-, 18-, and 24-month visits, parents will complete the PSI and PHQ-9 questionnaires.
 - At the 18- and 24-month visits, parents will also complete the ITSEA about their child.

4) STUDY EVALUATIONS AND MEASUREMENTS

a. Screening and Monitoring Evaluations and Measurements

i. Parent Adversity (ACE)

The 9 ACE questions query adults as to their exposure to 9 different adverse childhood experiences (economic hardship, domestic violence, parent mental health, discrimination, parent substance abuse, divorce, parent death, parent incarceration, and neighborhood violence) and are contained in the 2011-12 National Survey of Children's Health, a nationally representative telephone survey.

ii. Parent Health Literacy (SAHL)

The Short Assessment of Health Literacy (SAHL) is a validated measure of health literacy for English- and Spanish-speaking populations.

iii. Parent Depressive Symptoms (EPDS)

The Edinburgh Postnatal Depression Scale (EPDS) is a validated 10-item scale for postpartum depression symptoms with scores ≥ 9 having a sensitivity of 97% and specificity of 43% for major or minor depression.

iv. Reading Activity (StimQ)

The StimQ is an office measure of cognitive stimulation at home available in Spanish and English, and the Read subscale of the StimQ contains questions on the frequency of parent-child reading activity and the number and variety of books at home.²⁴ Psychometric analysis of the StimQ shows high internal consistency (Cronbach's Alpha=0.89) and test-retest reliability ($r=0.84$) and moderate correlation with the Bayley Scales of Infant Development ($r=0.52$, $p<0.001$).

We will also use a brief reading questionnaire (Appendix 12) about when participants began reading to their child and what influenced that decision.

v. Language Development (PLS)

The Preschool Language Scale-5th Edition (PLS) is a validated measure of expressive and receptive language function among children from birth through 7 years of age and is available in Spanish and English. The PLS has been standardized in over 1400 children nationally with a sensitivity of 0.83 and a specificity of 0.80 for the detection of language delay.

vi. Infant Toddler Social Emotional Assessment (ITSEA)

The ITSEA assesses for social or emotional problems and competencies in infants and toddlers and was designed to identify children with deficits or delays in these areas. It provides a comprehensive profile of problems and competencies with scores on 4 domains: 1) Externalizing 2) Internalizing 3) Dysregulation 4) Competence. Each domain is comprised of a number of subscales. The ITSEA also yields scores on three clusters that include atypical behaviors: Maladaptive, Social Relatedness, and Atypical.

vii. Patient Health Questionnaire – 9 (PHQ-9)

The Patient Health Questionnaire (PHQ) is a self-administered version of the PRIME-MD diagnostic instrument for common mental disorders. The PHQ-9 is the depression module, which scores each of the 9 DSM-IV criteria as “0” (not at all) to “3” (nearly every day). A PHQ-9 score ≥ 10 had a sensitivity of 88% and a specificity of 88% for major depression.

viii. Parenting Stress Index (PSI)

The PSI Short Form (PSI/SF) is a direct derivative of the Parenting Stress Index (PSI) full-length test. All 36 items on the Short Form are contained on the Long Form with identical wording and are written at a 5th-grade reading level, for parents of children 12 years and younger. The PSI/SF yields a Total Stress score from three scales: Parental Distress, Parent-Child Dysfunctional Interaction, and Difficult Child. Scores at or above the 85th percentile are considered high and Defensive Reponding scores at 10 or below are considered extremely low.

ix. Qualitative Measures

An interview guide with appropriate probes will be utilized to guide the semi-structured interviews. Areas that will be investigated include: understanding parent's perception of value in reading to their infant, factors that promote reading, and barriers that inhibit/limit reading. Elements of parent characteristics, family support and structure, and community factors will be explored through semi-structured interviews. As is typical in qualitative research, the order of questions and phrasing may change iteratively without changing content or risk. A purposive sample of parents as described previously in the section regarding the investigational plan will be selected to participate in the interviews. Interviews will be conducted with the goal to achieve

thematic saturation and elicit themes. The interviews will be recorded, transcribed, and stored on a secure CHOP server.

5) STATISTICAL CONSIDERATIONS

a. Primary Endpoint

The primary endpoint will be differences in PLS scores at 6 and 24 months of age.

b. Secondary Endpoints

Secondary endpoints will be the difference in StimQ scores at 6, 12, 18, and 24 months of age and the ITSEA scores at 18 and 24 months of age.

c. Statistical Methods

Summary statistics will be obtained, and differences between intervention and control groups will be assessed using intention-to-treat analysis. Cross-sectional differences in StimQ scores and PLS scores between intervention and control groups at the 6 and 24 month study visits and differences in ITSEA scores at 18 and 24 month study visits will be assessed using t-tests. To determine whether early literacy promotion is associated with greater language development, we will develop regression models using longitudinal data methods that adjust for correlation in PLS scores over time and for potential confounding by demographic characteristics. To explore whether early literacy promotion is associated with greater child socio-emotional development, we will develop regression models for scores at 18 and 24 months that adjust for potential confounding by demographic characteristics. To explore the impact of early literacy on healthcare utilization, the EHR will be reviewed to identify a subjects number of well visits and their vaccination history.

To determine whether parent adversity, health literacy, parenting stress, and/or depression modify the effects of early literacy promotion on language development, we will develop similar regression models using longitudinal data methods, but we will also fit interaction terms between study group and ACE score (≥ 4), SAHL (high or low), PSI score, and EPDS score (> 9) or PHQ-9 Score (> 4). To determine if parent-child reading activity mediates the association of intervention group assignment and language development, we will use mediation analysis with separate models regressing group assignment on language development, parent-child reading activity on group assignment, and group assignment on language development adjusted for parent-child reading activity.

Assuming a power of 0.90, an alpha of 0.05, a 20% loss to follow-up over two years, and a clinically significant difference of 4 points or more on the expressive and receptive subscales of the PLS between groups, we estimate that we will need to recruit a total sample size of 120 eligible children (60 in each group) to participate in the study. All analyses will be conducted using Stata Statistical Software, version 13 (College Station, TX).

We will use NVIVO software to assist in data management for the semi-structured interviews. This software facilitates thematic coding, the assessment of inter-rater reliability, and correlation of themes with demographic variables. After detailed review of each transcript, we will develop a coding scheme and dictionary. We will use the constant comparative method in which newly collected data are compared with categories that have emerged from previously collected data. Through an iterative process, we will discuss the emerging themes as a team and revise the interview guide as needed to explore in depth themes arising from the data. If differences in coding arise, two members will discuss the data and negotiate to reach a consensus. If consensus cannot be reached a third member will decide the outcome. Once thematic saturation is reached, findings will be shared with participants at a follow up focus group after interviews have been conducted.

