3.1.1 Screening Phase

Children who attend these clinics are primarily poor (72% Medicaid) and diverse racially with 80% being African-American, 10% white, 5% Hispanic, and 5% Asian. Children will be eligible to participate in this study if they were born ≥ 35 weeks estimated gestational age, without neurodevelopmental disabilities or congenital malformations, with Medicaid insurance (proxy measure for poverty), and < 30 days old at the time of enrollment. Children who are born premature < 35 weeks EGA, who have neurodevelopmental disabilities, or who have congenital malformations are at increased risk of language delays and will be excluded. In addition, we will exclude families who do not speak English or Spanish, as the main measures of reading activity (StimQ, Appendix 6) and language development (Preschool Language Scale-V, Appendix 7) are only available in English and Spanish.

Potential subjects will be identified at the time of their first well child visit < 30 days of life using the electronic health record (EHR). Eligible newborns' parents will be approached at the time of their child's appointment by research staff. They will obtain written informed consent from participants in private. Participants will be randomized to receive either the early literacy promotion arm or the standard literacy promotion arm based on random assignment.

Randomization sequences will be developed by the project biostatistician using computer-generated random numbers prior to study enrollment and will be placed in sealed opaque envelopes. Randomization will ensure equivalence between groups on measured and unmeasured characteristics and is considered to be the strongest protection against bias in study design. Written informed consent will be obtained prior to any study related procedures being performed in person. Consent will include a discussion of study rationale, procedures, measures, benefits, risks, and alternatives to participation. After consent, subjects will either be assigned to the literacy promotion arm or the standard literacy promotion arm of the study. Regardless of their assignment, once they have consented to participate, they will complete a demographic questionnaire (Appendix 1), questionnaires about adverse childhood experiences (Appendix 2), and health literacy (Appendix 3) and the Edinburgh Postnatal Depression Scale (EPDS) (Appendix 4) prior to the intervention.

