3.1.2 Study Treatment Phase (start of the study intervention)

Once recruited, newborns and their parent will be randomized into either the intervention or the control group. Children randomized to the early literacy promotion arm will receive developmentally appropriate books, information on the importance of early parent-child reading activity by pediatric clinicians, and weekly text message reminders concerning early literacy and daily reading activity at well child visits from one week to 6 months of age. Developmentally appropriate books will be selected for each well child visit prior to 6 months of age. Information on early literacy will be standardized and age-based and will be provided to parents by pediatric clinicians at well visits prior to 6 months of age. The weekly text message reminders will be initiated following enrollment, will be standardized, and will be scheduled according to parent preference in the morning, afternoon, or evening. The text message reminders will help remind parents to ensure that children in the intervention arm are exposed to parent-child reading activity in their first six months of life. Sample text messages are included in Appendix 5. In order to avoid any bias, parents of children in the control group will also receive weekly text messages focused about child safety instead of reading tips or advice. Beginning with the 6-month well child visit, children in this arm will receive the standard ROR Program as described in the standard literacy promotion group below.

Children randomized to the standard literacy promotion arm will receive developmentally appropriate books and information on the importance of parent-child reading activity by pediatric clinicians beginning with the 6-month well child visit and weekly text message reminders concerning child safety. This conforms to the ROR National Program recommendations and is considered standard of care at these 3 urban clinics. To prevent contamination in which pediatric clinicians inadvertently provide books and instruction on reading activity to control children prior to 6 months of age, a research assistant will ensure that books and reading instruction are not provided to children in this arm prior to 6 months of age. The weekly text message reminders will be initiated following enrollment, will be standardized according to age, and will be scheduled according to parent preference in the morning, afternoon, or evening.

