8.6.2 Gifts

Parents participating in the intervention will receive tote bags at their enrollment and four books over the course of the first four months of the study, one at each well visit (enrollment within first week of life, 1 month, 2 month, and 4 months). All parents will receive a small gift to thank them for participating at the end of the final study visit.

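### The enrolment visit appears to randomise before the baseline questionnaires are completed; the protocol should put the forms before the envelope

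*Combined protocol and SAP*

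**What the plan says.** Four places in the combined protocol and SAP bear on the order of events at enrolment.

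- **Study Procedures, part a (Screening/Consenting Visit and Study Visit 1).** After identification and consent, the list gives "Randomize newborns and their parents into intervention and control groups" and, directly below it, "Collect baseline demographic, parent adversity, and parent mental health information".
- **Section 3.1.1.** "After consent, subjects will either be assigned to the literacy promotion arm or the standard literacy promotion arm of the study". The next sentence begins "Regardless of their assignment, once they have consented to participate, they will complete a demographic questionnaire (Appendix 1" and goes on to the ACE, health literacy and depression forms. Its only timing condition is at the end: "Edinburgh Postnatal Depression Scale (EPDS) (Appendix 4) prior to the intervention".
- **Section 3.1.2.** "Once recruited, newborns and their parent will be randomized into either the intervention or the control group". No baseline step is placed between recruitment and randomisation.
- **Section 3.2.** The sequence is built from "computer-generated random numbers prior to study enrollment and will be placed in sealed opaque envelopes". The section heading includes blinding, but the text describes none.

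Arm-specific items are handed over at the same visit. Under section 8.6.2, "Parents participating in the intervention will receive tote bags at their enrollment", and the Study Procedures (part b) give the first book at enrolment.

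The Statistical Methods use the baseline data in two ways. ACE, SAHL and EPDS enter as interactions with study group, alongside PSI and PHQ-9. Demographic characteristics enter as adjustment covariates in the longitudinal PLS model.

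**The concern.** A variable measured before allocation cannot depend on the arm. A variable measured after the parent or the research staff know the arm can, and randomisation no longer guarantees its balance. Completing the forms before the intervention does not give that protection. Sealed envelopes conceal the sequence only until they are opened, and consent includes a discussion of the rationale and procedures, so a parent who learns the assignment may well know what it means.

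Two routes are open:

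- **Differential answering.** This is most plausible for the EPDS, a self-reported symptom scale. It is less plausible for the ACE items, which ask about past exposures, and for the SAHL, which is described as an assessment of health literacy.
- **Differential refusal.** A parent who dislikes the assignment may decline some or all forms. A child without ACE, SAHL or EPDS data drops out of the matching interaction model. A child without demographic data drops out of the adjusted PLS model unless missing covariates are handled, and the Statistical Methods give no method for that.

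At stake are the Aim 2 interactions, for which the Publication section plans a separate manuscript, and to a lesser degree the adjusted PLS analysis. Section 7.2 says childhood trauma and depressive symptoms are asked about only once, at baseline, so a baseline affected in this way could not be retaken.

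**Working it through.** **1. The order.** The plan gives no figure for this point, so the first check is textual. The procedures list puts randomisation immediately before baseline collection. Section 3.1.1 puts assignment after consent, then describes the forms in words that presuppose an assignment. Section 3.1.2 randomises on recruitment. No section puts the forms before allocation, and none withholds the arm from parents or from staff collecting baseline data. The text therefore leans towards randomising first without saying so outright.

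**2. Inputs for the size of the effect.**

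- From the Statistical Methods: 60 children per arm and 20% loss, so 60 × 0.8 = 48 analysed per arm.
- Assumed, because the documents do not give them: 10% to 20% of parents score ACE ≥ 4 (6 to 12 per arm), high-ACE children differ by g = 0.3 to 0.5 SD on the PLS, and three parents in one arm misreport because they know the arm, otherwise unrelated to outcome.

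**3. Headcount.** Three parents are 3/12 = 25% to 3/6 = 50% of that arm's high-ACE stratum. This counts people; it does not measure bias.

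**4. Bias from misreporting.** With no true interaction, the spurious interaction is the contaminated share of the receiving stratum multiplied by g.

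| Scenario | Prevalence | Share | × 0.3 | × 0.5 |
|---|---|---|---|---|
| Three high report low | 10% | 3/(54+3) = 3/57 | 0.016 | 0.026 |
| Three high report low | 20% | 3/(48+3) = 3/51 | 0.018 | 0.029 |
| Three low report high | 10% | 3/(6+3) = 3/9 | 0.10 | 0.17 |
| Three low report high | 20% | 3/(12+3) = 3/15 | 0.06 | 0.10 |

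**5. Precision.** In SD units, SE = √[(2/48) × (1/p + 1/(1−p))].

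- p = 0.10: √(0.0417 × 11.11) = 0.68
- p = 0.20: √(0.0417 × 6.25) = 0.51
- p = 0.40: √(0.0417 × 4.17) = 0.42

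The worst case is 0.167/0.68, about a quarter of one standard error. Under-reporting reaches at most 0.029/0.51, about 6%.

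**6. A second set of assumptions.** Take prevalence p of 20% to 40%, with a fraction s of 10% to 20% of true high scorers in one arm reporting low. The spurious interaction is g × ps/(ps + 1 − p). It runs from 0.3 × 0.02/0.82 = 0.007 to 0.5 × 0.08/0.68 = 0.059 SD, against standard errors of 0.42 to 0.51 SD.

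**7. Refusal and the adjusted PLS model.** Suppose three of 60 in one arm decline the demographic form and are dropped, and assume their children differ from the rest by 0.3 to 0.5 SD. That arm's mean moves by 3/60 × 0.3 = 0.015 to 3/60 × 0.5 = 0.025 SD. The standard error of a simple difference with 48 per arm is √(2/48) = 0.20 SD.

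**The case against.** The strongest reply is that the order is inferred. The procedures list is unnumbered and not reliably chronological: part b opens with interviews and a focus group, ahead of books given at enrolment. Section 3.1.1 also moves back and forth between consent and randomisation. Its stated trigger for the forms is consent, and the reference to assignment may mean only that both arms complete them. This stands. A reader might infer that the data are definitely collected after the envelope is opened; the documents do not say that. They do leave that order open and favour it, which is reason enough for an explicit sentence.

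Second, the main comparison is largely protected. A reader might infer that ACE, health literacy and depression are covariates in the language analysis and that the treatment effect is therefore biased. The Statistical Methods adjust only for demographics, whose answers are hard to shift, and the cross-sectional PLS t-tests use none of these variables. What remains is refusal, which affects the adjusted model only.

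Third, the mechanism is conjectural. It is not obvious why reading texts rather than safety texts would change answers about parental death or divorce, and section 8.6.1 pays both arms the same at enrolment. This stands for ACE and less so for EPDS.

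Fourth, Aim 2 is exploratory and its interactions are imprecise. This also stands and limits the severity.

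**Conclusion.** The concern holds in a limited form. The protocol appears to randomise before the baseline forms and states no blinding, so EPDS answers, and less plausibly ACE answers, could be given or withheld with knowledge of the arm. The exposed analyses are the exploratory group-by-ACE, group-by-SAHL and group-by-EPDS interactions and, through refusal only, the demographics-adjusted PLS model.

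The likely bias is small. On the three-parent scenario it is about 0.02 to 0.17 SD against an interaction standard error of about 0.5 to 0.7 SD. These figures rest on the assumed prevalence, prognostic effect and number of parents. The 25% to 50% share of a stratum might be read as the size of the bias, but it is a headcount on an assumed prevalence. Section 1.3 describes adversity as common in such communities; a higher prevalence would lower that share.

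The case for acting is that prevention is free and later repair is not possible. A reader might also infer that reordering the visit makes every moderator a true baseline variable. It does not: PSI and PHQ-9 are first collected at 12 months, after the whole early-promotion period, so they are post-randomisation variables whatever the order at enrolment.

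**What to change.** In section 3.1.1 and Study Procedures part a, set one explicit order:

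1. Written consent.
2. Demographic, ACE, SAHL and EPDS forms completed in REDCap.
3. Next sealed envelope opened.
4. Arm-specific materials (tote bag, first book) and text enrolment.

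Add a sentence saying that the envelope is opened only once the baseline forms are complete, and bring section 3.1.2 into line. Consent, randomisation and baseline collection already share one visit, and REDCap is already the study database, so this adds no visit, measure or staff.

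Separately, state in the Statistical Methods that interactions with PSI and PHQ-9 involve post-randomisation variables and will be interpreted as such.
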